#### Endpoints

**Primary Outcome Measure Title:** Feasibility and acceptability of HOLA

**Primary Outcome Measure Description:** As measured by meeting 100% of targeted sample (N = 30), with 20% or less of eligible subjects refusing to participate, 85% or more of participants completing the post-intervention assessment, and 80% or more of sessions attended by participants.

**Primary Outcome Timeframe:** Baseline to follow-up assessment (16 weeks).

**Secondary Outcome Measure Title:** Changes in neurocognitive impairment

**Secondary Outcome Measure Description:** As measured by the WAIS-IV Digit Span Processing and Trails Making Test A and B. The WAIS-IV Digit Span Processing is a summary score with the lower scores indicating increased cognitive impairment. For Trails Making Test A and B the primary score is the time to complete the task with higher times indicating increased cognitive impairment.

**Secondary Outcome Timeframe:** Baseline to follow-up assessment (16 weeks).

**Secondary Outcome Measure Title:** Changes in changes in activity, psychosocial functioning, or biomarkers of cognition.

**Secondary Outcome Measure Description:** As measured by GPAQ (activity); PHQ-9, GAD-7, Multidimensional Scale of Perceived Social Support (psychosocial functioning); and interleukin-15, irisin, adiponectin, BDNF, IGF-1, and VEGF (biomarkers of cognition). The GPAQ is a summary score with higher scores indicating increased activity levels. PHQ-9 is a summary score with higher scores indicating increased depression levels. The GAD-7 is a summary score with higher scores indicating increased anxiety levels. The Multidimensional Scale of Perceived Social Support is a summary score with higher scores indicating increased levels of perceived social support. Levels of interleukin-15,

IRB Study Number: 20201202  
Version 4.02, Date: 11/10/2021

irisin, adiponectin, BDNF, IGF-1, and VEGF are calculated from blood draws with well-defined average ranges.

**Secondary Outcome Timeframe:** Baseline to follow-up assessment (16 weeks).

**9) Data and Specimen Banking\***

Data will be collected with pre-programmed questionnaires. Data will be exported to SPSS for analysis. All electronic data will be stripped of identifiers and will be stored in password-protected files. For each data file, a code number will be assigned, and the master list, linking code numbers with names, will be stored separately. The data will be stored on password protected, network computer hard drives in the Department of Psychiatry and Behavioral Sciences, which will only be accessible to the PI.

Blood samples will be stored at the University of Miami Center for AIDS Research Laboratory Sciences Core (D) at -80 °C until analysis. The labels on the blood sample tubes will not contain *participant ID numbers*. The blood samples will be stored in locked freezers in locked rooms within access-limited sections of the building.

All the data will be stored and secured using the procedures outlined above. Access to records and participant data will be allowed only to the study personnel.

Study data request goes through a web-based check-in and check-out procedure implemented by CLaRO. The Data Manager or designee monitors the logs. Upon granting of the approval, the requester will either get the hard copy of the data or link to access the electronic data. All the data will not contain any identifying information.

**10) Data Management\***

As a pilot study, we will evaluate the feasibility of recruitment, assessment procedures, retention, acceptability, and implementation of HOLA in a sample of midlife and older Latinos LWH (**Aim 1**). Consistent with recommendations from biostatistical workgroups funded by NIH, this pilot study is not powered to test a hypothesis. This approach to analysis of feasibility data mirrors the structure of the first HOLA trial and other pilot trials conducted at the CNSA. Successful recruitment will be defined as meeting 100% of targeted sample (N = 30), with 20% or less of eligible subjects refusing to participate. Adequate retention will be defined as 85% or more of randomized subjects completing the post-intervention assessment. Acceptability is defined as 80% or more of sessions attended by subjects. To identify modifications needed in the design of a larger, confirmatory randomized controlled trial (**Aim 2**), we will use a project evaluation questionnaire developed by investigators at the CNSA and used in previous studies. The items are a mix of rating scales, yes/no questions, and open-ended questions that allow participants to give feedback in short

IRB Study Number: 20201202  
Version 4.02, Date: 11/10/2021

answer format with specific interest in understanding the participants' opinions regarding the specific components of the intervention. To explore changes in cognitive decline risk factors (waist circumference, dyslipidemia, hypertension, and glucose), psychosocial functioning (depression and anxiety severity, social support), and health-related quality of life (**Aim 3**), a one-way ANOVA will be used to illustrate the change in scores from baseline to post-intervention in all the outcome measures used.

A repeated measures ANOVA, as we have proposed, is appropriate to explore the intervention effects on cardiometabolic risk factors, psychosocial functioning, and health-related quality of life given that this type of analysis is often used in studies that investigate either changes in mean scores over three or more time points. In the exploratory analyses, we will use age, SES, and years of education as covariates. In addition, a list of current medications will also be collected at baseline. Should the participants' medications be dose-adjusted, changed altogether, or if they are started on new medications such as statins, then we will adjust for them in them in the exploratory analysis as well. Covariates will be tested as moderators of treatment response.

Maintenance of Confidentiality:

Our staff is CITI certified and trained with maintenance of confidentiality. The information provided by study participants will be held as personal and confidential to the extent permitted by law. In addition to the safeguards included as part of the recruitment and screening process by assigning a patient a study ID to de-identify participants, all study participants will be given the contact information for the Principal Investigators to answer any questions that may arise. Participants will be informed that they may end their participation at any time without affecting access to any other services they are currently receiving. All study procedures will be conducted according to good clinical practice and all other relevant regulatory guidelines.

All electronic data will be stripped of identifiers and stored in password-protected files on servers at the Department of Psychiatry and Behavioral Sciences. These data are password secured for minimal access to authorized personnel associated with the study. For each data file, a code number will be assigned, and the master list, linking code numbers with names, will be stored separately. At the conclusion of the project, the record linking the assigned research number and participant identity will be destroyed. Data will be entered into password secured databases by staff authorized by the principal investigator to do this, and they will abide by confidentiality regulations of the HSRO. No subject will be identified by any published report.

IRB Study Number: 20201202  
Version 4.02, Date: 11/10/2021

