**3) Objectives\***

The project will conduct a pilot single-arm trial with Latinos living with HIV (LWH) to assess feasibility, acceptability, and preliminary effects on cognition for a fully powered randomized trial (R01).

**Specific Aim 1:** To determine feasibility and acceptability of HOLA, adapted to incorporate a cognition focus, aimed at improving cognitive functioning among older Latinos LWH and incorporating activity tracking (Fitbit);

**Specific Aim 2:** To explore whether HOLA will produce changes in cognitive functioning between baseline and post-test (16 weeks);

**Specific Aim 3:** To explore whether HOLA will produce changes in activity, psychosocial functioning (depression, anxiety, social support) or biomarkers of cognition (myokines/cytokines [IL-15], adipokines [irisin and adiponectin], neurotrophic factors [BDNF, IGF-1 VEGF]) between baseline and post-test; and APOE e4 carrier status (a genetic risk for dementia) baseline only.

**Specific Aim 4:** To explore whether changes in activity, psychosocial functioning or cognitive biomarkers correlate with changes in cognition, while accounting for genetic risk for dementia (APOE e4 carrier status).

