**8) Procedures Involved\***

Participants will be assessed at two time points (baseline and post intervention at 16 weeks) on measures of neurocognitive and psychosocial functioning. Blood will be collected to determine APOE (baseline only) and biomarkers of cognition (baseline and 16-weeks).

All participants will read and sign an informed consent. They will initially be provided with a verbal summary of the study and for those who appear to have problems reading the consent form it will be read aloud. Participant payments will be graduated. Participants will receive \$25 on the first visit and \$35 on the second visit (total of honoraria = \$60). They will also be given the Fitbit tracking device to keep.

IRB Study Number: 20201202  
Version 4.02, Date: 11/10/2021

Prior to starting the baseline assessments, blood draws will take place at the CTRS. Approximately 20mL (2 tablespoons) of blood will be collected by a trained phlebotomist. Study staff will obtain biomarkers of cognition (myokines/cytokines [IL-15], adipokines [irisin and adiponectin], neurotrophic factors [BDNF, IGF-1 VEGF]) as well as apolipoprotein E (APOE) status, a genetic marker of dementia risk (baseline only).

Trained and certified bilingual research assistants (RAs) who have at least a bachelor's degree will conduct all assessments in private offices at the Soffer Clinical Research Building (CRB) or another location convenient to the participant where privacy can be protected. The neurocognitive testing will be conducted under the supervision of a neuropsychologist. Approximate administration time of the assessment will be 60 minutes.

IRB Study Number: 20201202  
Version 4.02, Date: 11/10/2021

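### Section 10 names two different procedures for the same baseline-to-week-16 change analysis; taken literally, the one-way ANOVA ignores pairing and gives wrong error bars

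*Combined protocol and SAP*

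**What the plan says.** The analysis plan sits in Section 10 (Data Management). It names the change analysis twice.

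- The Aim 3 sentence opens "To explore changes in cognitive decline risk factors (waist circumference, dyslipidemia, hypertension, and glucose), psychosocial functioning", adds quality of life, and ends: "a one-way ANOVA will be used to illustrate the change in scores from baseline to post-intervention in all the outcome measures used".
- The next paragraph says "A repeated measures ANOVA, as we have proposed, is appropriate" for exploring "the intervention effects on cardiometabolic risk factors, psychosocial functioning, and health-related quality of life", on the ground that "this type of analysis is often used in studies that investigate either changes in mean scores over three or more time points".

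The design is given elsewhere. Section 3 (Objectives) describes a single-arm pilot, and Section 8 (Procedures Involved) schedules two assessments of each participant, at baseline and at 16 weeks.

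The Endpoints part of Section 8 lists 13 secondary change measures: Digit Span, Trails A and Trails B; GPAQ; PHQ-9, GAD-7 and perceived social support; and six blood biomarkers.

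**The concern.** A one-way ANOVA and a repeated measures ANOVA are different procedures if each is run as named. The first compares independent groups. The second uses the fact that each participant supplies both values. An analyst who follows the first sentence to the letter would enter visit as a grouping factor and treat two readings from one person as readings from two people.

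The second sentence does not settle the matter. It gives a reason that does not fit a two-visit trial, and its outcome list omits cognition, activity and the biomarkers. Those outcomes are reached only by the closing words of the first sentence, which carries the unsuitable label.

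What is at stake is the precision reported for the exploratory outcomes. Section 3 makes preliminary effects on cognition, as groundwork for a powered randomized trial, a stated purpose of the pilot. The mean within-person change, its interval and the SD of change are the quantities that a later trial would draw on.

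**Working it through.** **Which outcomes each sentence names.** Both sentences in Section 10 list cardiometabolic or risk-factor measures, psychosocial functioning and quality of life. The risk factors for cognitive decline are spelled out as waist, lipids, blood pressure and glucose, so they are not cognitive tests. Against the Endpoints list:

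- Total: 3 cognitive + 1 activity + 3 psychosocial + 6 biomarkers = 13.
- Under a listed construct: PHQ-9, GAD-7 and social support = 3.
- Covered only by the catch-all: 13 − 3 = 10.

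Waist circumference, lipids, glucose and quality of life are neither endpoints nor entries under Assessment Measures.

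**Inputs for the size of the error.** The plan has no power or precision figure to reproduce. From the documents: 30 enrolled (Section 6) and a retention target of 85% (Endpoints), so 0.85 × 30 = 25.5, or at least 26 completers. Assumptions not in the documents: within-person correlation r, equal SDs at both visits (results are in SD units) and 95% intervals.

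**Formulas for the half-width.**

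- Paired, 26 pairs: t(0.975, 25) × √(2(1 − r)/26), with t = 2.060.
- Literal one-way, restricted to the 26 pairs: t(0.975, 50) × √(2/26) = 2.009 × 0.277 = 0.557.
- Literal one-way, all available values (30 baseline, 26 week 16): t(0.975, 54) × √(1/30 + 1/26) = 2.005 × 0.268 = 0.537.

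The third line matters because an analysis that treats visits as independent groups does not need pairs and would naturally use every value.

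| r | Paired half-width | One-way, 26/26 | One-way, 30/26 | One-way SE ÷ paired SE, 26/26 | Same, 30/26 | Coverage of one-way 95% CI, 26/26 | Same, 30/26 |
|---|---|---|---|---|---|---|---|
| 0.3 | 0.48 | 0.56 | 0.54 | 1.20 | 1.15 | 98.0% | 97.8% |
| 0.5 | 0.40 | 0.56 | 0.54 | 1.41 | 1.37 | 99.3% | 99.2% |
| 0.7 | 0.31 | 0.56 | 0.54 | 1.83 | 1.76 | 99.9% | 99.9% |

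The 26/26 SE ratio is 1/√(1 − r). Coverage comes from simulated bivariate-normal data; the paired interval covers 95% throughout.

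**Where the direction changes.** Setting the half-widths equal gives r = 1 − 13 × (h/2.060)², where h is the one-way half-width. With h = 0.557 this is 0.05; with h = 0.537 it is 0.12. Below those values the one-way interval is the narrower one. At r = 0 the half-widths are 0.56 (26/26) or 0.54 (30/26) against 0.57 paired, and one-way coverage is still 95%. At r = −0.2 one-way coverage falls to about 93%.

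**Unequal SDs.** With the week-16 SD between 0.75 and 1.5 times the baseline SD and 26 pairs, the SE ratio √((1 + k²)/(1 + k² − 2rk)), where k is the SD ratio, runs 1.18–1.20, 1.36–1.41 and 1.68–1.83 at r = 0.3, 0.5 and 0.7.

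**The point estimate.** With complete pairs, both procedures give the same mean change. With 30 baseline and 26 week-16 values, the one-way estimate is a difference between visit means over different sets of people, so the two can differ.

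**The case against.** The strongest reply is that the two labels are compatible. One-way counts the factors (time), and repeated measures says that the factor is within-person. The second sentence presents the method as already proposed, and the only earlier proposal in Section 10 is the one-way ANOVA. With one arm and two visits, a one-way repeated-measures ANOVA is the natural joint reading. It equals a paired t-test, and nothing is lost. This stands as an account of the likely intent. It does not remove the need to state it, because the only sentence that reaches cognition carries the bare one-way label.

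A second reply is that the catch-all wording does cover cognition, activity and the biomarkers. That is correct. A reader might infer that the plan has no analysis for cognition; the documents do not support that. What holds is that these ten measures are not named in either sentence.

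A reader might also infer that repeated measures ANOVA is invalid with two visits. It is not. The phrase about three or more time points is a misfitting rationale, and deleting it is editorial.

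Finally, the stakes are small. Sections 6 and 10 both say that the pilot is not powered for hypothesis tests. That stands, and it limits the severity.

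**Conclusion.** The inconsistency is real and minor. Section 10 should name one paired analysis; as written, its first label run literally gives wrong error bars. At r of 0.3 to 0.7, with equal SDs and 26 completers, the one-way half-width is 0.54 to 0.56 SD where the paired one is 0.48 down to 0.31 SD, and a nominal 95% interval covers about 98% to 99.9%. These figures rest on assumed values of r and apply only to the literal reading.

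A reader might go further and infer that the plan commits to an unpaired test, or that it risks false positives. Neither follows. The second sentence points to a within-person analysis, and for positive r the error is conservative. Only at negative r, which is hard to expect for repeat measurements on the same person, would the one-way interval cover too little. The effect is confined to exploratory secondary outcomes. Recruitment, refusal, retention and attendance, which make up the primary outcome, do not use this test.

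**What to change.** Replace the one-way ANOVA sentence in Section 10 with:

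> For every change outcome in the Endpoints section, including the cognitive tests, activity and the biomarkers, we will report the unadjusted mean within-person change (week 16 minus baseline) with 95% CI from a two-level repeated-measures ANOVA (equivalent to a paired t-test) in participants with both visits, stating n and the SD of change. The covariate-adjusted and moderator analyses are additional exploratory analyses of the same within-person changes.

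The last clause is needed because Section 10 also plans adjustment for age, SES, education and medication changes, and the equivalence to a paired t-test does not hold in general once covariates enter.

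Then make the outcome lists in both Section 10 sentences match the Endpoints, which removes waist circumference, lipids, glucose and quality of life, and delete the rationale about three or more time points.

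The cost is one replaced sentence and a few small edits, with no new data. The downside is that the analysis uses completers only: if 26 complete, 30 − 26 = 4 participants do not contribute. Stating n makes that visible.

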**6) Number of Subjects\***

30 older Latinos age 50+ will be enrolled. Consistent with recommendations from biostatistical workgroups funded by NIH, this pilot study is not powered to test hypotheses. The proposed project builds upon recruitment and intervention infrastructure that is being used in other HOLA studies. Participants will not be replaced if withdrawn or lost to follow-up.

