## 12) **Withdrawal of Subjects\***

If a subject finds the research procedures to be upsetting or aversive, they will have the option to withdraw from the study. Participation will be completely voluntary and will not affect the treatment they are receiving. Participants will be told that they may choose not to answer any questions and may decide to terminate the interview at any time. Research staff will be instructed to terminate interview sessions if participants appear to be stressed by the process. Additionally, the research staff will know how to link participants immediately with treatment personnel including case managers or therapists if participants appear to be stressed.

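### The two-visit change analyses name two different ANOVAs and no missing-data method; a mixed model on all 30 baselines would be less exposed to loss related to baseline (low priority)

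*Combined protocol and SAP*

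**What the plan says.** **Sample and visits.** Section 6 says "30 older Latinos age 50+ will be enrolled" and "Participants will not be replaced if withdrawn or lost to follow-up". Section 8 says "Participants will be assessed at two time points (baseline and post intervention at 16 weeks", with no condition on attendance at the walks.

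**Retention.** Section 10 says "Adequate retention will be defined as 85% or more of randomized subjects completing the post-intervention assessment". The trial has one arm, so this must mean enrolled subjects, as the Endpoints part of section 8 has it. Both places set attendance at sessions (80% or more) as a separate criterion.

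**Analysis.** Section 10 first names a one-way ANOVA of baseline-to-post change for all the outcome measures. The next paragraph says "A repeated measures ANOVA, as we have proposed, is appropriate to explore the intervention effects" and supports it by the use of that method with three or more time points. No section gives an analysis population, a method for missing scores or a sensitivity analysis for them.

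**Leaving.** Section 12 says "If a subject finds the research procedures to be upsetting or aversive, they will have the option to withdraw from the study". It also lets participants skip questions or end an interview. No section describes someone who stops walking but stays in follow-up.

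**The concern.** With two visits, a standard repeated measures ANOVA is an analysis of paired change. It cannot use a person who has no 16-week score, so that person's baseline contributes nothing to the estimate. If people with worse baselines are lost more often, the completers are not typical of the 30 enrolled and their mean change is shifted.

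The one-way wording does not solve this. Read literally, with visit as the factor, it compares all 30 baselines with the 16-week scores of those who returned. It also treats the two visits as independent groups.

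Section 3 says the pilot is meant to give preliminary effects on cognition for a fully powered randomized trial. The estimate therefore feeds a later design, and there is no control arm against which a shift caused by loss would show.

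**Working it through.** The plan gives no power, SD or effect size, so it has no figure of its own to reproduce here.

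**1. Missing scores the plan accepts.** 0.85 × 30 = 25.5, so 26 completers meet the target and 30 − 26 = 4 (13.3%) may be missing. If true retention were 80%, 85% or 90% (assumed), the chance of reaching 26 of 30 is 0.26, 0.52 or 0.83. More than 4 missing is therefore plausible.

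**2. Bias when loss depends on baseline.** Orient each score so that higher is better and use baseline SD units. Let the completers' mean baseline lie δ above the mean of all enrolled, let ρ be the correlation between visits, and let there be no true change.
- The completers' expected 16-week mean is ρδ above the common mean.
- Paired change in completers: ρδ − δ = −(1 − ρ)δ, which is apparent worsening by regression to the mean.
- One-way by visit (all baselines against completers' week 16): ρδ − 0 = +ρδ, which is apparent improvement.
- Likelihood estimate: the completers' week-16 mean is shifted by their regression slope to the mean of all 30 baselines, giving ρδ − ρδ = 0.

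**3. Numbers.** The documents give none of the following, so all are assumptions: 15% loss, odds of loss multiplied by 2.2 to 5 per SD worse baseline, ρ from 0.5 to 0.7. Simulated trials of 30 give:

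| Analysis | Bias (SD) | SE (SD) |
|---|---|---|
| Paired change, completers | 0.03 to 0.09, towards worsening | 0.15 to 0.20 |
| One-way by visit | about 0.05 to 0.13, towards improvement | up to 0.21 |
| Likelihood, all 30 baselines | about 0 | 0.15 to 0.20 |

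The formulas agree with these. The largest completer bias, 0.09 at ρ = 0.5, implies δ = 0.09 / 0.5 = 0.18, and then the one-way bias at ρ = 0.7 is 0.7 × 0.18 = 0.13. The smallest, 0.03 at ρ = 0.7, implies δ = 0.03 / 0.3 = 0.10, and then the one-way bias at ρ = 0.5 is 0.5 × 0.10 = 0.05. The completer bias is 0.21 to 0.46 of its SE.

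**4. Cost of ignoring pairing.** With 30 and 26 scores treated as independent, the nominal SE is √(1/30 + 1/26) = 0.27 SD. The true sampling SE is at most 0.21 SD.

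**5. Loss that depends on unseen change.** The completers' mean differs from the mean of all enrolled by (m/N) × (difference in change between completers and non-completers). With m = 4 and N = 30, and assumed differences of 0.25, 0.5 and 1.0 SD of change, this is 0.03, 0.07 and 0.13 SD. Where the difference is not explained by baseline, no model fitted to the observed scores removes it. Only testing those people at week 16 does.

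**The case against.** **Size and standing.** Section 10 says "this pilot study is not powered to test a hypothesis", the primary outcome is feasibility and acceptability, and the change analyses are exploratory. The odds of loss have no source in the documents; at 1.5 per SD the completer bias is only 0.02 to 0.03 SD, about 0.11 to 0.15 SE. Even at 2.2 to 5, the completers' nominal 95% interval covers 92.7% to 94.5%. Root mean squared error improves little with the likelihood estimate: from 0.214 to 0.199 at odds 5 and correlation 0.5, and from 0.156 to 0.154 at odds 2.2 and correlation 0.7. All of this stands, and it is why the priority is low. Nor does the mixed model deal with practice effects or time trends, which a single-arm design leaves uncontrolled.

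**Inference.** Dropping incomplete cases follows from the method and is not written in the plan. The repeated measures sentence itself concerns cardiometabolic, psychosocial and quality-of-life outcomes; cognition and biomarkers come in through the one-way statement, which covers all measures. That also stands, but it does not rescue the plan, since either ANOVA is biased under baseline-related loss.

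**A stronger reading to avoid.** A reader might infer that anyone who tires of the 48 walks (3 × 16) is lost from the results, so that change is estimated only in those who stayed with the programme. The documents do not say so. Section 8 sets no attendance condition for week 16, section 10 counts retention apart from attendance, section 12 gives an optional right to withdraw, and section 13 allows the exercise to be modified. The set analysed under repeated measures is the 16-week completers, who may include poor attenders.

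**Conclusion.** The point holds as a modest improvement in method. The plan names two analyses for two-visit data and does not say what happens to the up to 4 of 30 whose 16-week score may be missing with the retention target still met. Under the assumed loss, the two readings err in opposite directions: 0.03 to 0.09 SD towards worsening for paired completers, and about 0.05 to 0.13 SD towards improvement for one-way by visit. Each is below one SE, and a likelihood analysis avoids both at practically no loss of precision.

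A reader might also infer that using completers flatters HOLA. In the scenario examined, where people with worse baselines leave and nothing truly changes, it does the reverse. Inflation would need loss linked to poor unseen change, for which the documents give no evidence and which the mixed model would not cure. The feasibility and acceptability results do not depend on any of this.

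**What to change.** **Section 10.** Replace both ANOVA statements with one likelihood-based mixed model per outcome: visit as fixed effect, unstructured 2 × 2 covariance, all 30 baselines included. Report the paired change in completers as a sensitivity analysis. State that the model assumes loss depends only on observed scores, and report how many lack each 16-week score with their baseline values. If nobody is lost, the estimated change equals the paired mean change, so nothing is given up.

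**Section 12.** As a clarification in line with sections 8 and 10, state that anyone who stops the walks but has not withdrawn consent is still invited to the 16-week assessment and blood draw. Record stopping HOLA separately from withdrawing from the study.

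**Cost.** Wording in two sections and slightly more analysis work. Any added week-16 visits fall within the 30 already planned, and they support the 85% retention criterion.

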### Assessment Measures

Dementia Screen: The Telephone Interview for Cognitive Status (TICS) will be used to screen for dementia. A score of 30 or below indicates cognitive impairment.

Walking Ability: The 10-meter walk test will be used to evaluate walking ability, which has been used as a screening instrument to measure functional mobility and gait speed in physical activity interventions with older adults.

Demographics: The Center for Latino Health Research Opportunities (CLaRO) Demographics Form will be used to collect demographic information (e.g., gender, education, income, preferred language, country of origin, time in the US, etc.) and will include a list of all diagnosed medical conditions and medications.

Acculturation: The 24-item Bidimensional Acculturation Scale (BAS) will be used to measure acculturation.

Depression Severity: The 9-item Patient Health Questionnaire (PHQ-9) will be used to measure depression severity.

Anxiety Severity: The 7-item Generalized Anxiety Disorder (GAD-7) scale will be used to measure anxiety severity.

Social Support: Perceived social support will be measured using the 12-item Multidimensional Scale of Perceived Social Support (MSPSS).

Physical Activity: The 16-item Global Physical Activity Questionnaire (GPAQ) will be used to measure physical activity.

Processing Speed: Trails Making Test A will be used to measure processing speed.

Attention/Working Memory: The WAIS-IV Digit Span will be used.

Learning: Hopkins Verbal Learning Test-Revised (HVLT-R)

Memory: HVLT-R Delay

Verbal Fluency: Animal Fluency and Controlled Oral Word Association Test (COWAT)

Executive Function: Trails Making Test B

IRB Study Number: 20201202  
Version 4.02, Date: 11/10/2021

Motor: Grooved Pegboard (dominant and non-dominant)

Biomarkers of cognition: Myokines/cytokines (IL-15), adipokines (irisin and adiponectin), and neurotrophic factors (BDNF, IGF-1 VEGF)

Genetic risk factor for dementia (baseline only): Apolipoprotein E (ApoE)

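### In a single-arm trial, covariates can be explored as predictors of change but not as moderators of treatment response; the planned medication adjustment also needs a stated week-16 data source

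*Combined protocol and SAP*

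**What the plan says.** All in the combined protocol and SAP.

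- **Design.** Section 3) Objectives: "The project will conduct a pilot single-arm trial with Latinos living with HIV (LWH"), intended to inform a later randomized trial. Section 8) Procedures Involved: "Participants will be assessed at two time points (baseline and post intervention at 16 weeks) on measures of neurocognitive and psychosocial functioning".
- **Moderators.** Section 10) Data Management names age, SES and years of education as covariates in the exploratory analyses, then adds: "Covariates will be tested as moderators of treatment response". It gives no comparator and no method for this test.
- **Medications.** The same section says "a list of current medications will also be collected at baseline". If a drug is later switched, newly started or given at a different dose, "then we will adjust for them in them in the exploratory analysis as well".
- **Where medications are recorded.** Under Assessment Measures, the demographics form "will include a list of all diagnosed medical conditions and medications". No visit is named for that form.
- **Status.** Section 6) Number of Subjects: "this pilot study is not powered to test hypotheses". Under Endpoints, the primary outcome is feasibility and acceptability. Change in cognition is secondary: "As measured by the WAIS-IV Digit Span Processing and Trails Making Test A and B".

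**The concern.** A moderator of treatment response is a variable across which the effect of treatment differs. Showing that requires some knowledge of how participants would have changed without the treatment, and this trial observes no one without HOLA. If older or less educated participants improve more, the planned wording would let that be reported as HOLA working better for them. Because the pilot is meant to give preliminary effects for a randomized trial, such a statement could shape that trial's eligibility, stratification or subgroup hypotheses on evidence that cannot support it.

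The medication plan raises a separate and smaller question. Adjusting for changes after baseline requires a record of those changes, and the text states a collection time only for the baseline list. If nothing further is collected systematically, the adjustment would rest on whichever changes happened to be mentioned.

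**Working it through.** The plan gives no figure to reproduce on either point, and no numerical input is needed. The check sets the text against the design.

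**(a) Moderation**

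1. With two visits, each participant supplies one change score per outcome. A covariate-by-visit term is then the slope of that change score on the covariate.
2. Write the change for participant *i* as: change = natural course + retest gain (cognitive tests only) + effect of HOLA + error.
3. Taking slopes on a covariate X: observed slope = slope of natural course + slope of retest gain + slope of HOLA effect.
4. Moderation of treatment response is the last term alone. The data estimate only the sum, so there is one estimable quantity and two or three unknown components.
5. A randomized control arm would estimate the other components, and subtraction would leave the HOLA term. Several measurements before the intervention might give some information on natural course. This trial has neither.
6. The sum stays a sum however many participants are enrolled. More than 30 would make the slope more precise without separating its parts.
7. The slope is still a valid description of who changed more between the visits. The fault is in the label and the conclusion it invites.

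Whether retest gain applies depends on an unclear passage. The sentence in section 10 that sets out the change analysis lists cardiometabolic, psychosocial and quality-of-life outcomes under Aim 3, then ends by referring to all outcome measures. That may or may not include the cognitive tests. Natural course applies either way.

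**(b) Medication changes**

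| Place | What it gives |
|---|---|
| Section 10 | List at baseline; adjustment for later changes; no statement of how a change is detected or coded |
| Assessment Measures | Medications on the demographics form, visit not named; only APOE is marked as baseline only |
| Section 8 | Two assessment visits; does not assign named questionnaires to visits |
| Adverse Event Reporting | Interview items on injuries, unexpected medical events, emergency and hospital admissions and unplanned clinic visits; off-protocol contacts recorded |

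The adverse-event items could bring some medication changes to light, for example one made at an unplanned visit. A dose change or new prescription at a routine appointment need not appear in any of them. No systematic source after baseline is therefore stated, although one is not ruled out.

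**The case against.** **On (a).** The strongest reply is that this is a matter of wording. The analyses are labelled exploratory, the pilot disclaims power for hypotheses, and treatment response can be read loosely as change observed during treatment. On that reading no model or estimate is affected. It stands that nothing in the data or the fitting has to change, and that the plan does not itself draw a causal conclusion from this test. But calling an analysis exploratory or unpowered speaks to precision and error rates, and the problem here is what the quantity means. Section 10 also says the analysis will explore intervention effects on several outcomes, which makes the causal reading a natural one. It is fair to add that attribution to HOLA is uncertain for every before-after change in this trial; the moderator sentence is where that problem is most easily corrected.

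A reader might infer that the covariate analysis is invalid and should be removed. The documents do not support that: a predictor-of-change analysis suits the design.

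**On (b).** Only APOE is marked as baseline only, so repeating the demographics form at week 16 is compatible with the text. A detailed manual of operations is promised and could hold the form schedule. Section 8's silence on medications at week 16 shows little, because it does not mention them at baseline either. All of this stands and lowers confidence.

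Two stronger readings should be resisted. One is that medication changes will not be recorded; the text shows only that no systematic source is stated. The other is that the adjusted result would replace the unadjusted change; the plan nowhere says so and confines the adjustment to exploratory work.

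**Conclusion.** **(a) Wrong as written, minor to moderate.** One arm with two visits cannot identify moderation of a treatment effect, at this sample size or any other. The conclusion rests only on the stated design and on the ordinary meaning of moderation. It needs no assumption about effect size, correlation or significance level, and the documents give none from which a useful magnitude could be calculated. The weight is limited because the analysis is exploratory and the primary outcome is feasibility and acceptability.

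**(b) A data-collection gap worth closing, with lower confidence.** The plan commits to an adjustment without stating where the post-baseline information comes from. A reader might call this a second mismatch with the design. It is not one: a before-after trial can record medication changes and examine their influence, and the text leaves room for a week-16 list. Because medication change happens after baseline, the adjusted and unadjusted results answer different questions and are best shown together. That is advice on presentation, not a correction of anything the plan says.

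**What to change.** **(a)** In section 10, replace the moderator sentence with:

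> Age, SES and years of education will be explored as predictors of change from baseline to week 16, reported as estimates with confidence intervals and not interpreted as moderation of a treatment effect.

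Naming the three covariates also settles whether medication change, described just before the moderator sentence, was meant to be among them. The edit costs nothing in data or analysis. The downside is giving up any moderator claim until the randomized trial.

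**(b)** State that the medication list is repeated at the existing week-16 visit and how a change will be coded. Report how many participants had a change, and show the medication-adjusted result beside the unadjusted paired change. The cost is a few minutes per participant. If the list will not be repeated, drop the adjustment. If the manual of operations already schedules it, one sentence in section 10 saying so is enough.
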